#### **6.7.2. Antiseptic Therapy**

Participants must agree to daily use (throughout the entirety of the study) of one of the following over-the-counter treatments to the body areas affected with HS lesions: either soap and water, a dilute bleach bath, or a topical antiseptic wash containing chlorhexidine gluconate or benzoyl peroxide.

#### **6.7.3. Wound Care**

Concomitant use of wound care dressings on HS wounds is allowed; however, options are limited to alginates, hydrocolloids, and hydrogels.

#### **6.7.4. Analgesic Therapy**

Use of opioid analgesics is prohibited for 14 days prior to the baseline visit regardless of HS or non-HS reasons. During the study, concomitant use of opioid analgesics is also prohibited, except for tramadol as detailed below.

If a participant is on a stable dose/regimen of a non-opioid analgesic (PRN is not considered stable) for a HS-related condition or non- HS medical condition (e.g., osteoarthritis), the participant may continue the analgesic, provided the dose is stable for 14 days prior to baseline and is anticipated to remain stable throughout study participation.

If a participant's pain (HS-related or non-HS-related) worsens after baseline, they may initiate analgesic therapy at any time as follows:

**For HS-related pain, permitted analgesics are limited to:**

- Non-steroidal anti-inflammatory drugs (NSAIDs, such as Ibuprofen) as per local labeling; AND/OR
- Acetaminophen (paracetamol) as per local labeling; AND/OR
- If HS-related pain is uncontrolled with ibuprofen and/or acetaminophen at the above dosing regimens after the baseline visit, participants can be prescribed tramadol (at a dose of up to 100 mg by mouth every 4 hours), not to exceed 400 mg/24 hours.

Dose adjustments of ibuprofen, acetaminophen, or tramadol, and use of these analgesics on an "as needed" (PRN) basis for HS-related pain up to the maximum permitted dose and frequency, are allowed during the study.

All analgesics and dose adjustments will be captured in the source and on the appropriate eCRF.

**For Non-HS-related Pain:**

All other non-opioid analgesics and tramadol are allowed at the recommended or prescribed dose.

**6.7.5. Prohibited Therapy**

Participants who initiate the following treatments during study participation must have their study intervention discontinued:

- Phototherapy (PUVA and/or UVB)
- All biologic therapy with a potential therapeutic impact on the disease being studied, including but not limited to the following:
  - TNF  $\alpha$ blockers (adalimumab, etanercept, certolizumab, infliximab, golimumab)
  - IL 1 blockers (anakinra, canakinumab, rilonacept)
  - IL 6 blockers (tocilizumab, sarilumab)
  - IL 23 blockers (ustekinumab, guselkumab, tildrakizumab)
  - IL 17 blockers (secukinumab, ixekizumab, brodalumab)
  - CD20- directed cytolytic antibody (rituximab)
  - Inhibitor of B-Lymphocyte stimulator-specific (belimumab)
  - Integrin receptor antagonist (natalizumab)
  - Inhibitor of T cell activation (abatacept)
  - JAK inhibitor (systemic and topical)
- Any investigational agents for the treatment of HS.
- Any other systemic drug therapies for HS, including but not limited to MTX, cyclosporine, and retinoids.

- Concomitant use of oral antibiotic therapy for HS or inflammatory disorders. Systemic antibiotic use (including oral) is allowed for the treatment of AEs other than a worsening of HS.
- Oral or injectable corticosteroids for the treatment of HS, except for protocol-allowed intralesional rescue therapy as outlined in Section 6.7.1.
- Surgical or laser intervention for an HS lesion except as outlined in Section 6.7.1.

#### **6.7.6. Concomitant Corticosteroid use for Conditions Other than HS**

The use of systemic corticosteroids for indications other than HS should be limited to situations for which, in the opinion of the treating physician, there are no adequate alternatives. They should be used on a short-term basis, preferably for  $\leq 2$  weeks. Longer-term use of corticosteroids should be discussed with the medical monitor or designee and may require discontinuation of study drug. Intra-articular, or routes of delivery of corticosteroids such as inhaled, otic, ocular, nasal, or other routes of mucosal delivery are allowed throughout the study.

#### **6.7.7. Drugs Metabolized by Cytochrome P450**

In vitro studies have shown that IL-1 could impact cytochrome (CYP) enzyme expression and activities (Renton 2005; Abdel-Razzak 1993). As such, suppression of IL-1 $\alpha$  by bermekimab, a cytokine modulator, may potentially alter the hepatic metabolism and clearance of drugs that are substrates for CYP enzymes (FDA Guidance 2020). Therefore, upon initiation or discontinuation of bermekimab in patients being treated with CYP substrates with a narrow therapeutic index, monitoring of the effect (eg, warfarin) or drug concentration (eg, theophylline) is recommended and the individual dose of the drug may be adjusted as needed.

### **6.8. Intervention After the End of the Study**

No long-term extension is provided in this Phase 2 study. Participants and investigators will be informed that study intervention will not be made available to them beyond this protocol and that they should return to their treating physician for guidance

## **7. DISCONTINUATION OF STUDY INTERVENTION AND PARTICIPANT DISCONTINUATION/WITHDRAWAL**

### **7.1. Discontinuation of Study Intervention**

A participant's study intervention must be discontinued if:

- The participant withdraws consent to receive study intervention.
- The participant or their legally acceptable representative withdraws consent/assent for administration of study intervention.
- The investigator believes that for safety reasons or tolerability reasons (e.g., AE) it is in the best interest of the participant to discontinue study intervention.
- The participant has a serious adverse reaction that is related to an injection including a hypersensitivity reaction. In general, discontinuation of study intervention administration

must be considered for participants who develop a nonserious but severe injection-site reaction.

- The participant has a reaction resulting in myalgia and/or arthralgia with fever and/or rash (suggestive of serum sickness and not representative of signs and symptoms of other recognized clinical syndromes) after an injection of study intervention. These may be accompanied by other events including pruritus, facial, hand, or lip edema, dysphagia, urticaria, sore throat, and/or headache.
- The participant becomes pregnant or plans a pregnancy during the study period. Refer to Section 10.6.
- The initiation of protocol-prohibited medications, treatments, or interventions (outlined in Section 6.7) that have an impact on HS efficacy evaluations.
- The participant has a malignancy including squamous cell skin cancer. Consideration may be given to allow participants, who develop  $\leq 2$  basal cell skin cancers and who are adequately treated with no evidence of residual disease, to continue to receive study intervention.
- A systemic opportunistic infection.
- A recurrent or chronic serious infection.
- The participant is deemed ineligible according to the following TB screening criteria:
  - A diagnosis of active TB is made.
  - A participant has symptoms suggestive of active TB based on follow-up assessment questions and/or physical examination or has had recent close contact with a person with active TB and cannot or will not undergo additional evaluation.
  - A participant undergoing evaluation has a chest radiograph with evidence of current active TB and/or a positive QuantiFERON®-TB test result and/or 2 indeterminate QuantiFERON®-TB test results on repeat testing (refer to Section 8.2.8) (and/or a positive tuberculin skin test result in countries in which the QuantiFERON®-TB test is not approved/registered or the tuberculin skin test is mandated by local health authorities).
  - A participant receiving treatment for latent TB discontinues this treatment prematurely or is noncompliant with the therapy.
- The participant is unable to adhere to the study visit schedule or comply with protocol requirements.
- The participant has a reaction resulting in myalgia and/or arthralgia with fever and/or rash (suggestive of serum sickness and not representative of signs and symptoms of other recognized clinical syndromes) occurring 1 to 14 days after an injection of study intervention. These may be accompanied by other events including pruritus, facial, hand, or lip edema, dysphagia, urticaria, sore throat, and/or headache.
- The participant has his/her treatment assignment unblinded by the investigator.
- Sponsor decision.

Participants who decide to discontinue study intervention administration for reasons other than those outlined above must be interviewed by the investigator to determine if a specific reason for discontinuing study intervention can be identified. Participants should be explicitly asked about

the possible contribution of AEs to their decision to discontinue study intervention; investigators should confirm that any AE information elicited has been documented. If a participant elects to discontinue study intervention due to an AE, the event should be recorded as the reason for study intervention discontinuation, even if the investigator's assessment is that the AE would not require study intervention discontinuation. The reason for study intervention discontinuation must be documented in the eCRF and in source documents. Study intervention assigned to a participant who discontinues may not be assigned to another participant.

A participant will not be automatically withdrawn from the study if he or she must discontinue treatment before the end of the treatment regimen. Participants who discontinue study intervention but do not terminate study participation will continue to return for protocol-specified procedures and evaluations for approximately 5 weeks following the last administration of study intervention. The procedures and evaluations listed for the Early Termination Visit should also be performed approximately 5 weeks after the last administration of study intervention.

All procedures and evaluations must be conducted prior to a participant's withdrawal of consent.

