  - d. Within 2 months before the first administration of study intervention, have a negative QuantiFERON®-TB (or T-SPOT® for sites in Japan) test result, or have a newly identified positive QuantiFERON®-TB (or T-SPOT® for sites in Japan) test result (see laboratory manual) in which active TB has been ruled out and for which appropriate treatment for latent TB has been initiated before the first administration of study intervention. Within 2 months before the first administration of study intervention, a negative tuberculin skin test, or a newly identified positive tuberculin skin test in which active TB has been ruled out and for which appropriate treatment for latent TB has been initiated before the first administration of study intervention, is additionally required if the QuantiFERON®-TB test is not approved/registered in that country or the tuberculin skin test is mandated by local health authorities.

**NOTE:** A negative tuberculin skin test result (see Section 10.8) is additionally required if the QuantiFERON-TB® test is not approved/registered in the country in which this protocol is being conducted. The QuantiFERON®-TB (or T-SPOT® for sites in Japan) test and the tuberculin skin test are not required at screening for participants with a history of latent TB and ongoing treatment for latent TB, if active TB has been ruled out, and if appropriate treatment has been initiated/completed as described above in Inclusion Criterion 13a.

- e. Have a chest radiograph (both posterior-anterior and lateral views, or per country regulations where applicable), or a chest CT scan taken within 3 months before the first administration of study intervention and read by a qualified radiologist or pulmonologist, with no evidence of current, active TB or old, inactive TB.
14. Before randomization, a woman must be either:
    - Not of childbearing potential.

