**AND**

- (ii) with absence of ALL conditions (a), (b), (c) above during the period between the negative test result and the baseline study visit.

NOTES on COVID-related exclusion:

- The field of COVID-related testing (for presence of, and immunity to, the SARS-CoV-2 virus) is rapidly evolving. Additional testing may be performed as part of screening and/or during the study if deemed necessary by the investigator and in accordance with current regulations / guidance from authorities / standards of care.
- Precaution: for those who may carry a higher risk for severe COVID-19 illness, follow guidance from local health authorities when weighing the potential benefits and risks of enrolling in the study, and during participation in the study.

12. Criterion modified per Amendment 2.

12.1. Has a history of latent or active granulomatous infection, including histoplasmosis or coccidioidomycosis, before screening. Participants with radiographic evidence of possible prior histoplasmosis or coccidioidomycosis will be

excluded. Refer to Inclusion Criterion 13 for information regarding eligibility with a history of latent TB.

13. Has a chest radiograph or a chest CT scan within 3 months before the first administration of study intervention that shows an abnormality suggestive of a malignancy or current active infection, including TB.
14. Has ever had a nontuberculous mycobacterial infection or opportunistic infection (eg, cytomegalovirus, pneumocystis, aspergillosis).
15. Has 2 indeterminate (on repeat sampling) QuantiFERON -TB test results.
16. Has had major surgery (e.g., requiring general anesthesia and hospitalization) within 8 weeks before screening, or has not fully recovered from such surgery, or has such surgery planned during the time the participant is expected to participate in the study.

**NOTE:** Participants with planned surgical procedures to be conducted under local anesthesia may participate.

17. Has a transplanted organ (with exception of a corneal transplant >3 months before the first administration of study intervention).
18. Has known allergies, hypersensitivity, or intolerance to bermekimab or adalimumab or its excipients (refer to IB).
19. Criterion modified per Amendment 2.

19.1. Has previously received adalimumab. This criterion only applies to participants enrolling in Part 1 of the study, where adalimumab is one of the possible randomization arms. This criterion does not apply to participants enrolling in Part 2.

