20. The participant is deemed ineligible according to the following TB screening criteria:
  - A diagnosis of active TB is made.
  - A participant has symptoms suggestive of active TB based on follow-up assessment questions and/or physical examination or has had recent close contact with a person with active TB and cannot or will not continue to undergo additional evaluation.
  - A participant undergoing evaluation has a chest radiograph with evidence of current active TB and/or a positive QuantiFERON-TB® (or T-SPOT® for sites in Japan) test result (and/or a positive tuberculin skin test result in countries in which the QuantiFERON-TB® test is not approved/registered or the tuberculin skin test is mandated by local health authorities), unless active TB can be ruled out and appropriate treatment for latent TB can be initiated prior to the next study intervention administration and continued to completion (see also Section 8.2.8.1 and Section 10.8). Indeterminate QuantiFERON-TB® (or

borderline T-SPOT® for sites in Japan) test results should be handled as described in Section 8.2.8.1. Participants with persistently indeterminate QuantiFERON-TB® (or borderline T-SPOT® for sites in Japan) test results may continue without treatment for latent TB if active TB is ruled out, their chest radiograph shows no abnormality suggestive of TB (active or old, inactive TB) and the participant has no additional risk factors for TB as determined by the investigator. This determination must be promptly reported to the medical monitor or designee and recorded in the participant's source documents and initialed by the investigator.

- A participant receiving treatment for latent TB discontinues this treatment prematurely or is noncompliant with the therapy.
21. Has received an immunomodulating biology therapy within the previous 3 months of study intervention administration (including, but not limited to, anti-cytokine, anti-complement antibodies, anti-Ig antibodies, etc).
  22. Has received phototherapy or any systemic medications/treatments that could affect HS or IGA evaluations within 4 weeks of the first administration of any study intervention.
  23. Has any other active skin disease or condition (e.g., bacterial, fungal or viral infection) that could have interfered with assessment of HS.
  24. Has a draining fistula count of >20 at the baseline visit.

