A participant whose first QuantiFERON-TB® test result is indeterminate should have the test repeated. In the event that the second QuantiFERON-TB® test result is also indeterminate, the participant may be enrolled without treatment for latent TB if active TB is ruled out, their chest radiograph shows no abnormality suggestive of TB (active or old, inactive TB) and the participant has no additional risk factors for TB as determined by the investigator. For sites in Japan, a participant whose first T-SPOT® test result is borderline should have the test repeated. In the event that the second T-SPOT® (for sites in Japan) test result is also borderline, the participant may be enrolled without treatment for latent TB if active TB is ruled out, their chest radiograph shows no abnormality suggestive of TB (active or old, inactive TB) and the participant has no additional risk factors for TB as determined by the investigator. This determination must be promptly reported to the medical monitor or designee and recorded in the participant's source documents and initialed by the investigator.

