Participants who experience close contact with an individual with active TB during the conduct of the study must have a repeat chest radiograph, a repeat QuantiFERON®-TB (or T-SPOT® for sites in Japan) test, a repeat tuberculin skin test in countries in which the QuantiFERON®-TB test is not approved/registered or the tuberculin skin test is mandated by local health authorities, and, if possible, referral to a physician specializing in TB to determine the participant’s risk of developing active TB and whether treatment is warranted. Study intervention administration should be interrupted during the investigation. A positive QuantiFERON®-TB (or T-SPOT® for sites in Japan) test or tuberculin skin test result should be considered detection of latent TB. Participants with a newly identified positive QuantiFERON-TB® (or T-SPOT® for sites in Japan or tuberculin skin) test result must undergo an evaluation to rule out active TB and initiate appropriate treatment for latent TB. Appropriate treatment for latent TB is defined according to local country guidelines for immunocompromised patients. If no local country guidelines for immunocompromised patients exist, US guidelines should be followed, or the participant will be excluded from the study. If the QuantiFERON-TB® test result is indeterminate, the test should be repeated. For sites in Japan, a participant whose first T-SPOT® test result is borderline should have the test repeated. Participants should be encouraged to return for all subsequent scheduled study visits according to the protocol. Participants who discontinue treatment for latent TB prematurely or who are noncompliant with therapy must immediately discontinue further administration of study intervention and be encouraged to return for all subsequent scheduled study visits according to the SoA (Section 1.3).

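### The TB rules contradict each other on two indeterminate results (excluded, conditionally admitted and a mandatory stop), and Section 7.1 omits T-SPOT

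*Protocol*

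**What the plan says.** **Entry.** Exclusion Criterion 15 (Section 5.2) reads "Has 2 indeterminate (on repeat sampling) QuantiFERON -TB test results", with no qualification. Exclusion Criterion 20, in the same list, says that participants whose QuantiFERON (or, in Japan, T-SPOT) stays indeterminate or borderline on repeat "test results may continue without treatment for latent TB if active TB is ruled out", the chest radiograph is clear and the investigator finds no other TB risk factor. Section 8.2.8.1 agrees with Criterion 20: when the second QuantiFERON "test result is also indeterminate, the participant may be enrolled without treatment for latent TB if active TB is ruled out", under the same further conditions. It gives a parallel sentence for borderline T-SPOT.

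For a positive test, Inclusion Criterion 13d accepts a newly positive result where active TB is excluded and "for which appropriate treatment for latent TB has been initiated before the first administration of study intervention". Exclusion Criterion 20 counts a positive result against the participant "unless active TB can be ruled out and appropriate treatment for latent TB can be initiated prior to the next study intervention administration".

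**Stopping.** Section 7.1 says a participant's "study intervention must be discontinued if" any listed condition holds. One condition is a radiograph showing active TB "and/or a positive QuantiFERON®-TB test result and/or 2 indeterminate QuantiFERON®-TB test results on repeat testing (refer to Section 8.2.8". No exception follows, and T-SPOT is not named.

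**On study.** Section 8.2.8.2 covers close contact with active TB: "Study intervention administration should be interrupted during the investigation". A positive test is to be handled as latent TB, with active disease ruled out and treatment started. An indeterminate or borderline test is to be repeated.

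**The concern.** A site with a twice-indeterminate participant finds one criterion that forbids entry, one that permits it under conditions, a procedures section that permits it, and a stopping rule triggered by the same result. Section 5 allows no waivers, so whichever text the site follows, it departs from another.

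What is at stake is consistent safety conduct and consistent deviation reporting. Part 1 participants may receive adalimumab, and Section 2.3 names TB among that drug's important risks. SAP Appendix 4 counts entering without meeting criteria, and meeting withdrawal criteria without being withdrawn, as major deviations. A participant enrolled exactly as Section 8.2.8.1 allows could be put in either category.

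**Working it through.** No arithmetic applies; the check sets the rules side by side.

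| Place | Role | Two indeterminate QuantiFERON | Two borderline T-SPOT (Japan) | Positive test |
|---|---|---|---|---|
| Inclusion 13d | Entry | Not listed; only a negative or a treated newly positive result qualifies | Not listed | Allowed if active TB excluded and latent-TB treatment begun before *first* dose |
| Exclusion 15 | Entry | Excluded, no exception | Not named | Not addressed |
| Exclusion 20 | Entry | Allowed on three conditions | Allowed on the same conditions | Allowed if active TB excluded and latent-TB treatment can begin before *next* dose and be completed |
| 8.2.8.1 | Entry | May be enrolled on the same conditions | May be enrolled on the same conditions | Rule out active TB, start treatment |
| 7.1 | Stopping | Must stop, no exception | Not named | Must stop (QuantiFERON, or skin test where applicable) |
| 8.2.8.2 | On study | Repeat; silent on a second such result | Repeat; silent on a second such result | Rule out active TB, start treatment; silent on resuming |

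1. **Entry against entry.** Take someone with two indeterminate QuantiFERON results, a clear radiograph and no other risk factor. Exclusion 20 and Section 8.2.8.1 let that person in; Exclusion 15 does not. All three are entry rules, so none can be set aside as belonging to another phase.

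2. **Entry against stopping.** If enrolled, the same person matches the wording of Section 7.1. The bullet does not limit itself to results obtained after the first dose, and its lead-in calls these TB screening criteria.

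3. **T-SPOT.** Inclusion 13d, Exclusion 20 and Sections 8.2.8.1 and 8.2.8.2 all name T-SPOT for Japan. Section 7.1 names only QuantiFERON and the skin test. Read literally, an on-study positive QuantiFERON is a stopping trigger and an on-study positive T-SPOT is not.

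4. **Next and first.** The two positive-test exemptions are otherwise close in meaning. *First* dose suits an entry rule; *next* dose implies a participant already being treated.

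5. **The hold.** Section 8.2.8.2 never says whether dosing resumes after latent-TB work-up. Its one explicit order to stop study drug concerns participants who abandon, or do not comply with, latent-TB treatment. It prints the close-contact paragraph twice, once without the hold. Section 7.1 refers to Section 8.2.8, but Section 8.2.8.2 does not refer back.

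6. **Visits after a stop.** Section 7.1 follows participants who stop drug for about 5 weeks after the last dose. Section 8.2.8.2 encourages return for all later scheduled visits. SAP Section 5.3.2.1 uses observed data after a stop of this kind, and SAP Section 5.3.3 counts a missing Week 16 value as non-response. The two visit rules should therefore not disagree.

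**The case against.** The strongest reply is that Section 7.1 governs dosing after randomisation and the exclusion criteria govern entry, so each phase has its own rule. On that view Section 8.2.8.2 can be read with Section 7.1 as hold, then stop. This largely stands for dosing. A reader might infer from *next* in Exclusion Criterion 20 that the protocol holds two on-treatment rules giving opposite dosing decisions for a positive test. The documents do not support that. Criterion 20 sits under a heading about potential participants, *next* looks like a slip for *first*, and its *may continue* wording can be screening language, since Section 8.2.8.1 speaks of continuing with pre-randomisation procedures. The non-compliance sentence in Section 8.2.8.2 is not permission to continue either, because it still serves participants enrolled while on latent-TB treatment.

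The reply does not reach the conflict between Exclusion 15 and Exclusion 20 with Section 8.2.8.1, which lies wholly within the entry rules.

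One could add that Section 7.1 must mean new results only, since otherwise it would also stop those admitted with a treated positive test under Inclusion 13d. That is probably the intent, but the bullet does not say so.

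On T-SPOT, Japan sites are not unprotected. Section 8.2.8.2 holds dosing and requires work-up, and Section 7.1 still stops drug for diagnosed active TB or on the investigator's safety judgement. The omission is a wording gap.

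**Conclusion.** The point holds at low severity, as wording that is wrong as written. The entry rules contradict each other on two indeterminate QuantiFERON results, and the stopping rule as worded catches someone whom two of the entry texts admit. The T-SPOT omission, *next* for *first*, and the unfinished hold in Section 8.2.8.2 are lesser clarifications.

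No numerical size is given. The documents state no rate of indeterminate or positive results. The QuantiFERON test is scheduled only at screening in both parts, so the entry conflict can arise at routine screening, while on-study tests depend on close contact or clinical suspicion.

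A reader might infer a material effect on the HiSCR50 comparison, because follow-up of about 5 weeks from a last dose before about Week 11 (11 + 5 = 16) ends before Week 16. The documents do not support treating that as the size of this problem. The 5-week limit applies to every drug discontinuation, any missing responder for any reason has the same effect, and Week 16 is observed if participants attend as Section 8.2.8.2 encourages. Power and type I error are unaffected.

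SAP Section 1 records the decision to terminate the study on 14 October 2022. What remains to gain is consistent deviation classification and not carrying this text into a later protocol.

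**What to change.** - **One rule for two indeterminate or borderline results**, stated alike in Exclusion 15, Exclusion 20 and Sections 8.2.8.1 and 7.1. Either the result bars entry and stops drug, or it is accepted under the stated conditions in both places. The choice is medical, but entry and stopping must change together: relaxing Exclusion 15 alone would admit people whose result triggers a stop. If entry is allowed, Inclusion 13d should list the result too.
- **Section 7.1:** add T-SPOT for Japan to the TB bullet.
- **Exclusion 20:** change *next* to *first*, as in Inclusion 13d.
- **Section 8.2.8.2:** cross-reference Section 7.1 as the rule that decides whether held dosing stops or resumes, including after a second indeterminate or borderline result.
- **Follow-up:** state that participants stopped for a TB finding follow Section 8.2.8.2 and attend scheduled visits, at least through the primary-endpoint visit, instead of the 5-week limit in Section 7.1.

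The cost is one decision by the sponsor's medical team and a wording change or site clarification letter. The extra visits are already in the schedule and concern only those stopped for a TB finding.
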